#### 12.3.3 Secondary Endpoint Analysis

## 12.3.3.1 Absolute Change From Baseline in Sweat Chloride

Raw values and absolute change from baseline in sweat chloride at each visit of the Current Study Period will be summarized descriptively based on the 124 FAS overall. Descriptive statistics, including number of subjects, mean, SD, median, min, and max, along with the 95% CI based on Normal approximation, will be provided for the absolute change from baseline values. The mean (95% CI) of the absolute change from baseline values will be plotted.

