7.2 Sample Size and Power

No formal sample size calculations have been performed for this study. The study will enroll approximately 50 subjects to provide data for the assessment of long-term safety in the target patient population, as requested by a regulatory agency.

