8 ANALYSIS SETS

The following analysis sets are defined. Enrolled subjects are those who signed consent/assent form and had an enrollment date in the database.

All Subjects Set: All subjects who are enrolled or dosed in Study 124. This analysis set will be used for individual subject data listings and disposition summary tables unless otherwise specified.

Safety Set: All subjects who are exposed to any amount of study drug in Study 124. This analysis set will be used for all safety analysis unless otherwise specified.

Full Analysis Set: All subjects who are enrolled and dosed in Study 124. This analysis set will be used for all analysis of PD and exploratory endpoints unless otherwise specified.

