- For all safety parameters, if there are multiple measurements within a visit window, then 1) the record closest to the target day will be used; or 2) if there are multiple records with the same distance to the target day, the latest record will be used.
- If there are local lab results and central lab results at same visit point, then the central lab results will be used.

BMI, weight, and length will follow PD parameter visit window rules when evaluated as PD endpoints; they will follow safety parameter visit window rules when evaluated as safety endpoints. Their corresponding z-scores will be assigned analysis visit window rules the same as BMI, weight, and length, respectively.

For clinical laboratory, ECG and vital sign measurements collected on the date of the first dose of study drug, if it cannot be determined whether the measurement was taken before or after the first dose, scheduled measurements will be treated as pre-dose observations, and unscheduled measurements will be treated as post-dose observations.

If ETT visit happens on or after 10 days of last LUM/IVA dose and there are no SFU assessments collected, then ETT Visit will be mapped to SFU Visit.

Incomplete/missing data will not be imputed, unless specified otherwise.

Outliers: No formal statistical analyses will be performed to detect or remedy the presence of statistical outliers, unless specified otherwise.

Multiplicity: No multiplicity adjustment will be performed, and there is no hypothesis testing.

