10.4 Secondary Endpoint Analysis

10.4.1 Absolute Change from Baseline in Sweat Chloride

For each subject and at each time point, two sweat chloride measurements will be collected: one from the right arm and one from the left arm. Of the two measurements, only sweat chloride values obtained from sample volume $\geq 15~\mu L$ will be included in any analysis as a sample volume of at least 15 μL is required for testing. If a subject has replicated measurements at a postbaseline time point, then the median of the values will be used in data analyses. If the sweat chloride values for the left and right arms are both from sample volume $\geq 15~\mu L$, these values will be averaged together for the analysis; if only one arm is from sample volume $\geq 15~\mu L$, only that value will be used. Any sweat chloride values outside of the reportable range (i.e., < 10~mmol/L or > 160~mmol/L) will not be included in the analysis.

Raw values and absolute change from baseline in sweat chloride at each visit will be summarized descriptively (n, mean, SD, SE, median, minimum, and maximum) based on the FAS. In addition, the 95% confidence interval (CI) based on Normal approximation of the absolute change from baseline values will be provided. The mean (95% CI) of the absolute change from baseline at each scheduled time point will be plotted.

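### The 95% CI for the sweat chloride change should use the t quantile; the Normal approximation, read as 1.96 × SE, is slightly too narrow

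*SAP*

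**What the plan says.** The secondary endpoint is the absolute change from baseline in sweat chloride. SAP 10.4.1 plans a 95% CI "based on Normal approximation of the absolute change from baseline values will be provided", next to n, mean, SD, SE, median, minimum and maximum at each visit. It adds: "The mean (95% CI) of the absolute change from baseline at each scheduled time point will be plotted". Protocol 12.3.3.1 has the same method: "along with the 95% CI based on Normal approximation, will be provided for the absolute change from baseline values". Neither document says whether the multiplier is 1.96 or a t quantile.

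The analysis uses the Full Analysis Set, defined in SAP 8 as "All subjects who are enrolled and dosed in Study 124", so rollover and LUM/IVA-naïve subjects are pooled. On size, SAP 7.2 states "No formal sample size calculations have been performed for this study" and "The study will enroll approximately 50 subjects to provide data for the assessment of long-term safety in the target patient population". On inference, SAP 10.1 states "No multiplicity adjustment will be performed, and there is no hypothesis testing".

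The visit schedules differ by group. After Day 1, protocol Table 3-1 has rollover subjects tested at Weeks 24, 48 and 96 (and at early termination). Table 3-2 adds Weeks 4 and 12 for LUM/IVA-naïve subjects. The window tables in SAP Appendix A follow the same pattern.

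SAP 10.5 also plans 95% CIs for growth, fecal elastase-1, IRT and fecal calprotectin, without naming a method.

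**The concern.** The interval is for the mean of one sample whose SD is estimated from that sample. Under Normal data the exact multiplier is the t quantile on n − 1 degrees of freedom. The value 1.96 is its limit as n grows, so at any finite n it gives an interval that is too short and covers less than its label says.

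With no hypothesis test planned, this CI and the SE are the only statements of uncertainty about the secondary endpoint, and the CI is drawn at every scheduled time point. A second issue is consistency. One set of CIs has a Normal-approximation label and the exploratory ones have no label, so a programmer could properly use z for sweat chloride and t for the other endpoints in the same report.

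**Working it through.** **Inputs.**
- Planned n of about 50: SAP 7.2.
- Two-sided 95% level: SAP 10.4.1.
- Multiplier under the natural reading: z = 1.95996. This is an assumption, because the documents print none.
- Number contributing at each visit: not given. Values of n other than 50 are illustrative.
- SD of the change: not given. A range of 10 to 20 mmol/L is assumed, only to put the effect in units.

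The plan states no SD, CI width or coverage, so there is no planned figure to reproduce.

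**Formulas.** For Normal data with estimated SD:
- coverage of mean ± z × SE = 1 − 2 × P(t with n−1 df > z)
- relative width of the t interval = t(0.975, n−1) / z
- added half-width in mmol/L = (t − z) × SD / √n

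**Results.**

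| n | t(0.975, n−1) | t / z | Coverage of the z interval | Added half-width, SD 10 to 20 mmol/L |
|---|---|---|---|---|
| 50 | 2.0096 | 1.0253 | 94.4% | 0.07 to 0.14 |
| 40 | 2.0227 | 1.0320 | 94.3% | 0.10 to 0.20 |
| 30 | 2.0452 | 1.0435 | 94.0% | 0.16 to 0.31 |
| 20 | 2.0930 | 1.0679 | 93.5% | 0.30 to 0.60 |
| 10 | 2.2622 | 1.1542 | 91.8% | 0.96 to 1.91 |

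At n = 50, for example, the half-width is 1.960/√50 = 0.277 SD with z and 2.010/√50 = 0.284 SD with t. A simulation of 200,000 Normal samples per n agrees: the z interval covers 94.4% at n = 50, 94.1% at n = 30 and 91.9% at n = 10.

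**Which row applies.**
- Weeks 24, 48 and 96 pool both groups, so n starts near 50. It falls with missed tests, because missing data are not imputed (SAP 10.1), and with withdrawals, who are not replaced (protocol 9.10).
- Weeks 4 and 12 rest on the LUM/IVA-naïve subjects alone. The rollover/naïve split is not stated. The nearest figure is the minimum of 10 per age group enrolled in Study 122B before naïve enrollment opens, which is 20 over the two groups. If exactly 20 rolled over, 50 − 20 = 30 would be naïve; more rollovers would mean fewer. This too is an assumption.

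**What t does not repair.** With moderately skewed data (lognormal, sigma 0.5) at n = 50, the simulated z interval covers 93.5% and the t interval 94.0%. Of a shortfall of 1.5 points, t recovers about 0.5. The rest comes from skewness.

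**The case against.** The strongest reply has four parts.

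1. **No multiplier is printed.** The phrase could loosely describe an ordinary Normal-theory interval for a mean, which is computed with t, and standard software gives t by default. The outputs may therefore already be right. This stands as a limit: 1.96 is the natural reading, not a stated fact. It also supports naming the method.
2. **The effect is negligible at the planned size.** At n = 50 it is 0.6 points of coverage and 2.5% of width. This stands.
3. **Nothing depends on the interval.** There is no test, success rule or stopping rule, the primary objective is safety, and n, mean and SE are tabulated, so a reader can form the t interval. This stands, and it holds the point at the lowest severity.
4. **The t interval is exact only for Normal data.** This stands, as the skewed-data check shows.

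A reader might go further and infer that the plotted error bars are seriously too short, with coverage near 92%. The documents do not support that. No visit is shown to have 10 or 20 children. A time point is lost to sweat volume only when neither arm reaches 15 µL; otherwise the valid arm is used (SAP 10.4.1). Subjects who stop treatment are asked to stay for assessments through Week 96 (protocol 9.1.4). Some may move early to commercial drug, but no attrition rate is given.

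None of this makes the stated method preferable. It limits only how much the choice matters.

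**Conclusion.** The point holds as a minor improvement to the specification. If the Normal approximation means 1.96 × SE, the interval labelled 95% covers 94.4% at n = 50 and 94.0% at n = 30 under Normal data. It would fall to 93.5% or 91.8% only if about 20 or 10 children contributed. Weeks 4 and 12 are the most plausible place for that, but the naïve count is not in the documents.

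The conclusion rests on two assumptions: that 1.96 is intended, and that the changes are roughly Normal. It does not undermine the secondary endpoint, and the protocol and SAP do not contradict each other on it. Severity: nice to have.

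**What to change.** - In SAP 10.4.1, replace the Normal-approximation wording with: 95% CI = mean ± t(0.975, n−1) × SE, where n is the number of subjects with a change value at that visit.
- In SAP 10.5, state the same method for the growth, fecal elastase-1, IRT and fecal calprotectin CIs.
- In SAP 3.1, which now records only typographical and administrative changes, list this as a change from protocol 12.3.3.1.

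The cost is a short SAP amendment and slightly wider intervals: 2.5% at n = 50 and 4.4% at n = 30. No visit, sample or data collection changes. The t interval does not correct for skewness, so the median and range already planned should be read beside it.

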10.5 Exploratory Endpoint Analysis

10.5.1 Absolute Change from Baseline in Growth Parameters

Absolute Change from Baseline in BMI-for-Age Z-score and BMI

BMI z-score will be calculated by using WHO BMI-for-age charts. The BMI-for-age z-score will be calculated as follows:

$$z = \begin{cases} \frac{\left(\frac{X}{M}\right)^{L} - 1}{LS} &, L \neq 0 \\ \frac{\ln\left(\frac{X}{M}\right)}{S} &, L = 0 \end{cases}$$

Where X is the derived BMI value in kg/m² based on the raw weight and raw height and L, M, and S are selected from the WHO BMI-for-age charts by subject sex and age. The BMI-for-AGE z-score tables contain these parameters by sex and age; they are available at (accessed Jun 09, 2023):

https://www.who.int/toolkits/child-growth-standards/standards/body-mass-index-for-age-bmi-for-age

Raw values and absolute change from baseline in BMI and BMI-for-age z-score at each visit will be summarized descriptively (n, mean, SD, SE, median, minimum, and maximum) based on the FAS. In addition, the 95% CI of the absolute change from baseline values will be provided. The mean (95% CI) of the absolute change from baseline values will be plotted at each scheduled visit.

Absolute Change from Baseline in Weight-for-Age Z-score and Weight

Weight-for-age z-score will be calculated by using WHO weight-for-age tables. The same equation used to calculate BMI-for-age z-score will be used to calculate weight-for-age z-score, where X in the equation will be the collected weight. L, M, and S parameters will be selected from the WHO weight-for-age tables. The weight-for-age z-score tables contain these parameters by sex and age; they are available at (accessed Jun 09, 2023):

• https://www.who.int/tools/child-growth-standards/standards/weight-for-age Weight-for-age z-score and weight will be analyzed in a similar way to BMI-for-age z-score and BMI.

Absolute Change from Baseline in Length/Height-for-Age Z-score and Length/Height

Length-for-age z-score will be calculated by using WHO length-for-age tables. The same equation used to calculate BMI-for-age z-score will be used to calculate length-for-age z-score, however X in the equation will be the collected length. L, M, and S parameters will be selected from the WHO length -for-age tables. The length-for-age z-score tables contain these parameters by sex and age; they are available at (accessed Jun 09, 2023):

• https://www.who.int/tools/child-growth-standards/standards/length-height-for-age See Appendix G Computing Z-Scores Using WHO Standards for further details on determining length/height and necessary adjustment.

Length/height-for-age z-score and length/height will be analyzed in a similar way to BMI-for-age z-score and BMI.

Absolute Change from Baseline in Weight-for-Length Z-Score

Weight-for-length z-score will be calculated by using WHO weight-for-length tables. The same equation used to calculate BMI-for-age z-score will be used to calculate weight-for-length z-score, where X in the equation will be the collected weight. L, M, and S parameters will be selected from the WHO weight-for-length/height tables. The weight-for-length z-score tables contain these parameters by sex and length/height; they are available at (accessed Jun 09, 2023):

• https://www.who.int/tools/child-growth-standards/standards/weight-for-length-height

See Appendix G Computing Z-Scores Using WHO Standards for further details on determining length/height and necessary adjustment.

Weight-for-length z-score will be analyzed in a similar way to BMI-for-age z-score.

10.5.2 Absolute Change from Baseline in Markers of Pancreatic Function Absolute Change from Baseline in FE-1 Levels

Raw values and absolute change from baseline in FE-1 levels at each visit will be summarized descriptively (n, mean, SD, SE, median, minimum, and maximum) based on the FAS. In addition, the 95% CI of the absolute change from baseline values will be provided.

In addition, the number and percentage of subjects with FE-1 levels consistent with pancreatic insufficiency (defined as FE-1 level <200 mg/kg) will be provided at baseline and at each visit.

The number and percentage of subjects with shift changes from baseline at each visit will be summarized using the following two categories: <200 mg/kg; ≥200 mg/kg.

The mean (95% CI) of the absolute change from baseline in FE-1 values will be plotted at each scheduled visit.

Absolute Change from Baseline in Serum IRT Levels

Raw values and absolute change from baseline in serum IRT levels at each visit will be summarized descriptively (n, mean, SD, SE, median, minimum, and maximum) based on the FAS. In addition, the 95% CI of the absolute change from baseline values will be provided.

The mean (95% CI) of the absolute change from baseline in serum IRT values will be plotted at each scheduled visit.

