# 11.3 Exploratory Assessments

### 11.3.1 Growth Parameters

Weight and length/height will be assessed and BMI will be derived. Length/height and weight must be measured with the subject in a dry diaper or dry underclothes only. If the subject is >2 years of age and can stand unassisted and follow directions, standing height should be measured; otherwise recumbent length should be measured. Length should be measured while the subject is supine by measuring from the crown of the head to the bottom of the feet, with the hips and legs straightened. BMI will be calculated using the following equation: BMI (kg/m²) = body weight (kg) ÷ stature² (m²). Z-scores adjusting for age and sex in weight, length/height, and BMI, as well as weight-for-length z-score will be derived. Formulas for calculating z-scores will be provided in the statistical analysis plan (SAP).

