Appendix G Computing Z-Scores Using WHO Standards

Adjusting Length/Height for Recumbent vs. Standing Position

In calculation of z-scores relating to length/height, an adjustment may be necessary depending on how the length/height data were collected and the child's age (World Health Organization, 2006; Schumacher, 2020).

If the Measures are KNOWN to Be Either Recumbent Length or Standing Height:

- If the subject's age is ≤ 24 Months (730 days), measure of recumbent length should be used. If standing height measure is collected instead, **0.7 cm must be ADDED** to the standing height measure to adjust.
- If the subject's age is > 24 Months (730 days), measure of standing height should be used. If recumbent length measure is collected instead, **0.7 cm must be SUBTRACTED** from the recumbent length measure to adjust.

If the Measures are **UNSPECIFIED** to Be Either Recumbent Length or Standing Height:

- If AGE at the Visit is Not Missing
 - o If child age is \leq 24 Months (730 days), the measure is to be considered as recumbent length
 - o If child age is > 24 Months (730 days), the measure is to be considered as standing height
- If Age at the Visit is Missing
 - o If the measure is < 87cm, it is to be considered as recumbent length
 - o If the measure is ≥ 87 cm, it is to be considered as standing height

If necessary, all ages collected in months can be converted to days using 1 month = 30.4375 days.

Linear Interpolation of Length/Height Measurements

The WHO standard tables for Weight-for-Length/ Height comes with tabulated Length/Height (X) values with 1 decimal place and at 0.1 intervals. In practice, if the collected Length/Height (X) values fall between the intervals, the following interpolation approach is suggested to obtain the appropriate values for L, M, and S (World Health Organization, 2006):

- 1. Round the **Length/Height** (X) to the nearest 1 decimal place value lower than the collected value (e.g., round 73.265 to 73.2), and obtain the L, M, and S values using the standard table. Let us denote the rounded value as (X_l) and the tabulated values as L_l , M_l , and S_l .
- 2. Round the **Length/Height** to the nearest 1 decimal place value higher than the collected value (e.g., round 73.265 to 73.3), and obtain the *L*, *M*, and *S* values using

the standard table. Let us denote the rounded value as (X_u) and the tabulated values as L_u , M_u , and S_u .

3. Obtain the interpolated values of L, M, and S as:

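### SAP 10.5.1 uses raw height for the BMI-for-age z-score, in conflict with the 0.7 cm recumbent/standing correction in Appendix G

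*SAP*

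**What the plan says.** Protocol 11.3.1 leaves the z-score formulas to the SAP, so the SAP text governs.

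- **BMI-for-age, SAP 10.5.1.** In the LMS formula, X is a BMI "based on the raw weight and raw height". The paragraph does not refer to Appendix G.
- **Length/height-for-age and weight-for-length, SAP 10.5.1.** Both send the reader to Appendix G "for further details on determining length/height and necessary adjustment".
- **Appendix G, scope.** "In calculation of z-scores relating to length/height, an adjustment may be necessary", depending on how the child was measured and on age. BMI-for-age is neither named nor excluded at this point.
- **Appendix G, rule.** If a child aged 24 months or less was measured standing, "0.7 cm must be ADDED". If an older child was measured lying down, "0.7 cm must be SUBTRACTED".
- **Protocol 11.3.1, measurement.** Standing height is for children over 2 years who can manage it; "otherwise recumbent length should be measured". Protocol 11.4.4 is looser and ties the switch to standing partly to whether the child is at ease with it.

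**The concern.** Three z-scores in SAP 10.5.1 depend on stature. Two are linked to the correction for measuring position. The third, BMI-for-age, is told to use raw height. A programmer working from the endpoint's own paragraph would have good reason to leave the correction out.

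The correction exists because the same child measures longer lying down than standing, and the WHO reference changes position at 24 months. The study spans that age: LUM/IVA-naïve children start at 12 to <24 months and reach roughly 34 to 46 months at Week 96. Toddlers who cannot yet be measured standing after their second birthday are to be expected.

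Without the correction, one child at one visit could have one stature behind weight-for-length and another behind BMI-for-age. BMI-for-age is summarised and plotted with 95% CIs at each visit, and there is no control arm in which a systematic shift would cancel.

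**Working it through.** The plan gives no figure for this effect, so there is none to reproduce. The check is the size of the shift if the correction is omitted.

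**Inputs**
- Correction: 0.7 cm (Appendix G).
- BMI = weight / stature² (Protocol 11.3.1).
- z = ((X/M)^L − 1)/(L·S) (SAP 10.5.1).
- Stature H: 87 cm as the central value, the only stature cut-off in Appendix G; 80 to 100 cm assumed as the range.
- S for BMI-for-age: not in the documents; 0.07 to 0.10 assumed.

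**Step 1: error in BMI at H = 87 cm**
- Recumbent length used as height, over 24 months: (87/87.7)² − 1 = −1.59%.
- Standing height used as length, 24 months or less: (87/86.3)² − 1 = +1.63%.

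**Step 2: shift in z near the median.** For X close to M, the size of the shift is about 2·ln((H + 0.7)/H)/S.

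| H (cm) | 2·ln((H + 0.7)/H) | S = 0.07 | S = 0.08 | S = 0.09 | S = 0.10 |
|---|---|---|---|---|---|
| 80 | 0.0174 | 0.25 | 0.22 | 0.19 | 0.17 |
| 87 | 0.0160 | 0.23 | 0.20 | 0.18 | 0.16 |
| 100 | 0.0140 | 0.20 | 0.17 | 0.16 | 0.14 |

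The range is 0.14 to 0.25. Letting L run from −1.5 to 1 and the child's true z from −2 to 2 (both assumed) widens it to about 0.10 to 0.31.

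**Step 3: change from baseline.** The error in the change is the error at the visit minus the error at baseline.
- Baseline correct, later visit recumbent after 24 months: change too low by about 0.2.
- Recumbent after 24 months at baseline, standing later: change too high by about 0.2.
- Recumbent after 24 months at both: the errors nearly cancel. With S = 0.08 and growth from 87 to 95 cm, 0.20 − 0.18 leaves about 0.02.

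The last two cases can arise. Rollover children were 12 to <24 months old when treatment began in Study 122B and had 24 weeks of treatment there. Using Appendix G's conversion, 24 × 7/30.4375 = 5.5 months, so a child who began at about 18.5 months or older (24 − 5.5) is past 24 months at the Study 124 baseline.

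**Step 4: visit mean.** At 0.2 z per affected child and a correct baseline, the mean change moves by 0.2 × 0.10 = 0.02 if 10% are mismatched and 0.2 × 0.30 = 0.06 if 30% are. The documents give no basis for choosing a share.

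**The case against.** The strongest reply is that Appendix G already covers BMI-for-age. Its opening scope is general, its wording is mandatory, and BMI is computed from height. The missing cross-reference is weak evidence of an exemption: the weight-for-age paragraph does not cite Appendix G either, yet the appendix applies its adjustment beyond ±3 SD to both weight-for-age and BMI-for-age by name. Nor is an unadjusted-sounding input decisive, since the length-for-age paragraph starts from length as collected and is then modified by Appendix G.

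This stands to a point. A reader might infer that the z-scores will certainly be biased; the documents do not support that, because Appendix G can be read to apply. But that reading sets Appendix G against the word raw in 10.5.1. It also leaves unexplained why BMI-for-age is named in the tail adjustment and not in the 0.7 cm rule. The SAP supports two derivations and does not choose between them.

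The second reply is that the matter is small. The endpoint is exploratory and descriptive, and no hypothesis is tested. With 50 children and an assumed SD of change of 0.8 to 1.0, the 95% CI half-width is 1.96 × SD/√50 = 0.22 to 0.28, well above a mean shift of 0.02 to 0.06. This stands, and it sets the weight of the point.

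**Conclusion.** The point holds as an internal conflict in the SAP with minor impact. Followed literally, 10.5.1 omits a correction that Appendix G calls for, and the protocol makes the affected measurements foreseeable.

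Per affected visit near the median BMI, the shift is about 0.14 to 0.25 z, given stature of 80 to 100 cm and S of 0.07 to 0.10. It is negative for recumbent length after 24 months and positive for standing height at or before 24 months. The second case is less likely, since Protocol 11.3.1 reserves standing height for children over 2 years and only 11.4.4 leaves room for it earlier.

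A reader might also infer that every child crosses 24 months on study, so that the change from baseline is biased in one known direction. That does not follow. Some rollover children are already past that age at the Study 124 baseline. Crossing it creates no error unless the measuring position is wrong, and the change is biased only when the mismatch differs between the two time points. The net effect on a visit mean depends on an unknown share of mismatched children. No safety conclusion rests on it.

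**What to change.** In SAP 10.5.1, state that for the BMI-for-age z-score stature is first adjusted per Appendix G, while BMI itself is still reported from raw values. In Appendix G, name BMI-for-age among the z-scores to which the 0.7 cm rule applies. If raw height is intended for this z-score, say so and give the reason.

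The correction works only where the measuring position is recorded; where it is not, Appendix G infers the position from age and no correction follows.

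The cost is one sentence in 10.5.1 and a phrase in Appendix G, by SAP amendment if the plan is already approved. The rule is already specified for the other two stature-based z-scores, so no new method is needed.
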